12.3 Adverse Events of Special Interest (AESIs)

Specific treatment-emergent AESIs, including important identified risks, will be identified by the search criteria provided in [Table 3](#).

Table 3. Adverse Events of Special Interest

Adverse Event of Special Interest	MedDRA Search Criteria/Codes
Important Identified Risks	
Pleural Effusion	PTs: 10035598 Pleural Effusion 10003522 Aspiration Pleural Cavity 10063045 Effusion
Pericardial Effusion	PTs: 10034474 Pericardial Effusion 10007610 Cardiac Tamponade 10034471 Pericardial Drainage 10063045 Effusion
Generalized Edema	PT 10018092 Generalised Oedema
Photosensitivity Reaction	PT 10034972 Photosensitivity Reaction
Important Potential Risks	
Pneumonitis	PTs: 10035742 Pneumonitis 10035745 Pneumonitis Chemical 10037765 Radiation Pneumonitis 10066728 Acute Interstitial Pneumonitis 10022611 Interstitial Lung Disease
Other AESIs	
Ascites	PT 10003445 Ascites

Table 3. Adverse Events of Special Interest (Continued)

Adverse Event of Special Interest	MedDRA Search Criteria/Codes
Cutaneous Reaction	
SOC 10040785 Skin and Subcutaneous Tissue Disorders
 
The observed TEAEs under this SOC will be medically adjudicated to maintain a list of PTs that are not medically relevant and that will be excluded from the analysis.
 
Current list of PTs to exclude:
 
10001760 Alopecia
 
10002424 Angioedema
 
10011985 Decubitus Ulcer
 
10014080 Ecchymosis
 
10020642 Hyperhidrosis
 
10051235 Madarosis
 
10070533 Nail Bed Disorder
 
10028694 Nail Disorder
 
10062283 Nail Ridging
 
10028692 Nail Discolouration
 
10029410 Night Sweats
 
10034754 Petechiae
 
10037087 Pruritus
 
10052576 Pruritus generalised
 
10037549 Purpura
 
10042682 Swelling Face

Thrombocytopenia	SMQ 20000031 Haematopoietic Thrombocytopenia (broad)
Haemorrhages	SMQ 20000039 Haemorrhage Terms (Excluding Laboratory Terms; narrow)
Edema	
PTs:
 
10030095 Oedema
 
10030124 Oedema Peripheral
 
10048961 Localised Oedema
 
10018092 Generalised Oedema
 
10042674 Swelling
 
10016807 Fluid Retention
 
10016803 Fluid Overload
 
10024770 Local Swelling
 
10048959 Peripheral Swelling
 
10007196 Capillary Leak Syndrome
 
10015993 Eyelid Oedema
 
10016029 Face Oedema
 
10052139 Eye Oedema
 
10034545 Periorbital Oedema

Table 3. Adverse Events of Special Interest (Continued)

Adverse Event of Special Interest	MedDRA Search Criteria/Codes
Hypoalbuminemia	PTs: 10020942 Hypoalbuminaemia 10005287 Blood Albumin Decreased 10005286 Blood Albumin Abnormal
Hepatotoxicity	SMQs: 20000007 Drug-Related Hepatic Disorders (severe events only; broad) 20000009 Cholestasis and Jaundice of Hepatic Origin (broad) 20000008 Liver Related Investigations, Signs and Symptoms (broad) Exclude PT 10020942 Hypoalbuminaemia from this search since hypoalbuminemia is associated with chronic liver disease and therefore not included in AESI
Anemia	SMQ 20000029: Haematopoietic Erythropenia (broad)
Neutropenia	SMQ 20000030: Haematopoietic Leukopenia (broad)
Infusion-Related Reaction	PT 10051792 Infusion related reaction
Nephrotoxicity	SMQ 20000003 Acute Renal Failure (broad)
Teratogenicity/Embryotoxicity	SMQ 20000185: Pregnancy and Neonatal Topics (broad)
Abuse Liability*	CMQ: 80000120 Abuse Liability
Febrile Neutropenia (Symptomatic Neutropenia)**	PTs: 10016288 Febrile Neutropenia 10049151 Neutropenic Sepsis 10059482 Neutropenic Infection

* Search performed as needed for the Drug Abuse Liability Assessment (DALA) report.

** Search performed for only patient narratives for specific safety assessments.

Time to onset

Time to onset is the Rx Day of the start date of the first occurrence of AESI. If a subject has not experienced an AESI, the subject will be censored on the day of the subject's last assessment (i.e., the day of the subject's last known laboratory assessment, last known vital sign assessment, last known physical exam, last known tumor assessment, or last known follow-up visit, whichever is the latest) or 70 days from the last study drug administered, whichever is earliest; if the subject has not experienced an AESI and had no

post-baseline assessment (i.e., none of laboratory assessment, vital sign assessment, physical exam, or tumor assessment), the subject will be censored on the day of the subject's first study drug.

Median onset time will be estimated using a Kaplan-Meier method with corresponding 95% CI for the median for each treatment arm.

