**Appendix I. CTCAE v 4.0 Grading of Relevant AEs**

Group	Adverse Event	Grade 1	Grade 2	Grade 3	Grade 4
Serosal Effusions	Ascites	Asymptomatic; clinical or diagnostic observations only; intervention not indicated	Symptomatic; medical intervention indicated	Severe symptoms; invasive intervention indicated	Life-threatening consequences; urgent operative intervention indicated
	Definition: A disorder characterized by accumulation of serous or hemorrhagic fluid in the peritoneal cavity.				
	Pericardial effusion	–	Asymptomatic effusion size small to moderate	Effusion with physiologic consequences	Life-threatening consequences; urgent intervention indicated
	Definition: A disorder characterized by fluid collection within the pericardial sac, usually due to inflammation.				
	Pericardial tamponade	–	–	–	Life-threatening consequences; urgent intervention indicated
	Definition: A disorder characterized by an increase in intrapericardial pressure due to the collection of blood or fluid in the pericardium.				
	Pleural effusion	Asymptomatic; clinical or diagnostic observations only; intervention not indicated	Symptomatic; intervention indicated (e.g., diuretics or limited therapeutic thoracentesis)	Symptomatic with respiratory distress and hypoxia; surgical intervention including chest tube or pleurodesis indicated	Life-threatening respiratory or hemodynamic compromise; intubation or urgent intervention indicated
	Definition: A disorder characterized by an increase in amounts of fluid within the pleural cavity. Symptoms include shortness of breath, cough and marked chest discomfort.				
	Capillary leak syndrome	–	Symptomatic; medical intervention indicated	Severe symptoms; intervention indicated	Life-threatening consequences; urgent intervention indicated
	Definition: A disorder characterized by leakage of intravascular fluids into the extravascular space. This syndrome is observed in patients who demonstrate a state of generalized leaky capillaries following shock syndromes, low-flow states, ischemia-reperfusion injuries, toxemias, medications, or poisoning. It can lead to generalized edema and multiple organ failure.				
Edema	Edema face	Localized facial edema	Moderate localized facial edema; limiting instrumental ADL	Severe swelling; limiting self-care ADL	–
	Definition: A disorder characterized by swelling due to excessive fluid accumulation in facial tissues.				

Group	Adverse Event	Grade 1	Grade 2	Grade 3	Grade 4

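### SAP Table 3 removes the preferred term Swelling Face from Cutaneous Reaction but does not list it under Edema, so events coded to it are missed in the Edema AESI summaries

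*SAP*

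**What the plan says.** SAP Section 12.3 identifies treatment-emergent AESIs through the search criteria in Table 3. Two rows matter here.

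- **Cutaneous Reaction** is the whole Skin and Subcutaneous Tissue Disorders class, less the PTs judged irrelevant: "The observed TEAEs under this SOC will be medically adjudicated to maintain a list of PTs that are not medically relevant". Under the label "Current list of PTs to exclude" the table names 16 PTs. They include "10002424 Angioedema" and, as the last entry, "10042682 Swelling Face".
- **Edema** is a closed list of 14 PTs. It includes "10016029 Face Oedema", "10042674 Swelling" and "10034545 Periorbital Oedema".

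Protocol Appendix I has an Edema group of its own. Its first entry is Edema face, defined as "A disorder characterized by swelling due to excessive fluid accumulation in facial tissues".

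SAP Section 12.3 also derives a time to onset for AESIs. Subjects without the AESI are censored, and the median is estimated by Kaplan-Meier for each arm.

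**The concern.** Removing Swelling Face from a skin search is reasonable in itself, since swelling from fluid is not a skin reaction. The difficulty is that the term is then assigned nowhere. Two reports of the same clinical picture can be treated differently: coded as Face Oedema the event is an Edema AESI, and coded as Swelling Face it is not.

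This falls on a toxicity that the protocol watches closely. Protocol Section 3.5 reports drug-related peripheral edema at 29.1%, and Section 6.1.8.4 mentions a small number of fatal events of generalized edema. At stake are the count of subjects with an Edema AESI and the onset curve for that AESI.

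**Working it through.** The plan gives no figure to reproduce, so the check is a comparison of term codes within SAP Table 3, followed by a comparison with the protocol.

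**Step 1. Is Swelling Face listed anywhere by PT?** Three sets were formed from Table 3:

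- PTs excluded from Cutaneous Reaction: 16
- PTs that define Edema: 14
- distinct PTs listed for inclusion in any row, Edema included: 34

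The overlap of the 16 excluded PTs with the 14 Edema PTs is 0. Their overlap with the 34 is also 0. Swelling Face (10042682) is therefore in no row defined by PTs. The generic term Swelling has a different code (10042674) and does not cover it. Angioedema (10002424) is in the same position.

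**Step 2. Does the omission fit the pattern of the Edema row?** The row lists oedema terms together with their swelling counterparts:

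| Oedema term listed | Swelling term listed |
|---|---|
| Oedema | Swelling |
| Localised Oedema | Local Swelling |
| Oedema Peripheral | Peripheral Swelling |
| Face Oedema | none; Swelling Face appears only among the skin exclusions |

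Eyelid, Eye, Periorbital and Generalised Oedema also stand without a swelling partner. For the face, however, Table 3 itself shows that a separate swelling PT exists.

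**Step 3. Does it fit the protocol?** Appendix I defines Edema face by swelling and puts it in the Edema group. An event that meets this definition can fall outside the SAP's Edema AESI through the choice of near-synonym alone.

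**Step 4. How does Table 3 treat a similar removal?** Hypoalbuminaemia is taken out of the Hepatotoxicity search. There the table gives a reason specific to that term, and the term has its own AESI row. Swelling Face has neither.

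**Step 5. Which results change?**

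- Subjects missed in the Edema count = subjects with Swelling Face and none of the 14 listed PTs.
- The same subjects are censored in the Edema time-to-onset summary instead of counted as events.
- A subject with Swelling Face first and a listed Edema PT later is still counted, but with the later onset day.

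The documents give no frequency for Swelling Face and no split between it and Face Oedema, so none of these can be given a number.

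**The case against.** The case on the other side is substantial, and much of it stands.

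- **Scope.** A reader might infer that facial swelling as such belongs to no AESI. The documents do not support that. Face, Eyelid, Eye and Periorbital Oedema are all in the Edema row, so the gap is one PT. Absence from every AESI can also be verified only for rows defined by PTs, because the contents of the standardised and custom MedDRA queries used in other rows are not in the documents.
- **Coding practice.** Events are lost only if reported terms are coded to Swelling Face. The protocol's grading term is Edema face, which may steer reports toward the captured PT, and the sponsor's coding guideline is cited but not available. An actual undercount is therefore not shown; what is shown is that the search would miss such events.
- **Visibility.** SAP Section 12.2 tabulates all treatment-emergent events by system organ class and PT for each arm. Swelling Face and the full skin class count remain in view.
- **Dosing.** A reader might link the gap to dose decisions, because Protocol Table 6 refers to Appendix I for the edema group. Those decisions rest on toxicity graded by the investigator. SAP Table 3 is a reporting search and does not affect them.
- **Pruning after the fact.** The trial is open-label, and the skin list is called current and maintained from observed events, so a reader might infer that it can be narrowed once results by arm are known. SAP Section 4.0 says the SAP will be finalized before any comparative analysis by arm. Photosensitivity Reaction, the identified skin risk, has its own row that pruning cannot reach. What remains is that Table 3 does not say outright that finalization closes the list.

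None of this explains why Swelling Face is left out of Edema while its near-synonym and the other swelling terms are in.

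**Conclusion.** The point holds as a small gap in specification. Followed as written, Table 3 leaves events coded to PT 10042682 out of the Edema AESI count and treats the affected subjects as event-free, or as later in onset, in the time-to-onset summary. This rests on the code lists in Table 3 and on the Edema face entry in Appendix I, with no numerical assumption.

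The size cannot be estimated from the documents. Any figure would need an assumed rate of facial swelling, an assumed coding split and an assumed overlap with other edema terms. Overlap could be considerable given how common peripheral edema is, and Oedema Peripheral is listed. The effect is confined to the AESI summaries; general adverse event reporting and efficacy are untouched. The missing statement on closing the skin list is secondary.

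**What to change.** 1. Add PT 10042682 Swelling Face to the Edema row of SAP Table 3.
2. Decide at the same time whether Angioedema (10002424), also excluded from Cutaneous Reaction and absent from Edema, belongs in an AESI, and record the decision.
3. As a minor addition, state that the Cutaneous Reaction exclusion list is fixed at SAP finalization, before any tabulation by arm.

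The cost is one code, one recorded decision and one sentence, in a SAP that still describes itself as a draft. No new data are needed. A separate display of the full skin class count is unnecessary, since SAP Section 12.2 already provides it by arm.

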### **3.5 Benefits and Risks**

Activity of the current second line standard of care topotecan is suboptimal and high unmet need in this setting is widely recognized. Based on the Phase 1 results of rovalpituzumab tesirine, this agent may offer improved efficacy over current second line standard. This study will assess the efficacy, tolerability, and safety of rovalpituzumab tesirine in SCLC subjects with first disease progression during or following front-line platinum-based chemotherapy (e.g., cisplatin or carboplatin plus etoposide).

The most frequent treatment-emergent adverse event (TEAE) terms considered related to rovalpituzumab tesirine have included fatigue (37.6%), pleural effusion (29.4%) peripheral edema (29.1%) and decreased appetite (27.3%), while the most frequent,

related TEAE groups of Grade 3 is thrombocytopenia (10.3%), pleural effusions (6.2%), and anaemia (5.4%). In addition, preclinical toxicology studies conducted in the rat and the cynomolgus monkey have identified bone marrow, lung, liver and kidney as potential sources of clinical adverse events (AEs) (AbbVie Stemcentrx data on file). Accordingly, safety assessments will include regular assessments at protocol-specified time points of routine physical examination, laboratory and imaging tests, echocardiograms, a fluid retention questionnaire, daily weights, and spot urine protein testing.

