**Additional Two Cycles of Rovalpituzumab Tesirine (Arm A only)**

Up to two additional cycles of rovalpituzumab tesirine may be permitted, however the last dose on study must be administered no later than 04 December 2019 for subjects in Arm A who provide consent and who satisfy all of the following criteria:

- achieved clinical benefit defined as stable disease or better with two initial cycles of rovalpituzumab tesirine
- have findings indicative of disease progressing (not limited to CNS) at least 12 weeks after the second dose of rovalpituzumab tesirine
- received no other systemic anti-cancer therapy after two initial cycles of rovalpituzumab tesirine
- had no prior on-study serosal effusions (Appendix I) or edema of > Grade 2 or other non-hematological treatment-related AEs of  $\geq$  Grade 3 or potential DILI and any treatment-related AEs have resolved to Grade 1 or baseline
- have no clinically significant symptoms or signs related to disease progression and/or indicating threat to vital organs and no disease progression at critical anatomical sites necessitating urgent alternative treatment
- have no decline in performance status as compared to the last radiographic assessment at which no progressive disease was identified

Any new or progressing CNS disease of such subject must be definitively treated (radiotherapy or surgery) in order for the subject to be eligible for the two additional cycles of treatment. Subjects remaining in rovalpituzumab tesirine treatment post-progression not limited to CNS will be followed radiographically until the second event of progressive disease. CT/MRI scan must be performed within one week prior to the 4th dose of rovalpituzumab tesirine.

Subjects who do not provide consent for two additional doses of rovalpituzumab tesirine should proceed to the End of Treatment (EOT) visit before continuing on to the Survival Follow Up period.

The last radiographic assessment prior to additional doses of rovalpituzumab tesirine will be used as a new baseline for purposes of subsequent disease assessment.

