5.2 Design Diagram

This is a Phase 3, randomized, open-label, multinational, and multicenter study comparing the efficacy, safety and tolerability of rovalpituzumab tesirine versus topotecan in subjects with advanced or metastatic DLL3^{high} SCLC who have first disease progression during or following front-line platinum-based chemotherapy. DLL3^{high} is defined as $\geq 75\%$ tumor cells staining positive according to the VENTANA DLL3 (SP347) IHC Assay.

Eligible subjects will be randomized in a 2:1 ratio to receive rovalpituzumab tesirine (Arm A) or topotecan (Arm B):

[figure not shown]
- Subjects assigned to Arm A will receive 0.3 mg/kg rovalpituzumab tesirine (IV) on Day 1 of a 42-Day cycle for 2 cycles, along with 8 mg orally (PO) of dexamethasone twice daily on Day –1, Day 1, and Day 2. Regimen of Arm A will be administered for the 2 cycles planned unless earlier discontinuation is warranted due to disease progression, unacceptable toxicity or any other

reason. Up to two additional cycles of rovalpituzumab tesirine may be permitted for subjects in Arm A meeting certain criteria, as described in Section 5.3.1.1 of the study protocol.

- Arm B subjects will receive 1.5 mg/m² topotecan (IV) on Days 1 – 5 of each 21-Day cycle. Topotecan may be administered at a lower dose if required by the local label. The Arm B regimen will be administered until disease progression, unacceptable toxicity or any other reason requiring treatment discontinuation.

A schematic of the study is provided in Figure 1 Study Schema.

Figure 1. Study Schema

Empty arrowhead = Rovalpituzumab tesirine administration cycle; Dotted arrowhead = Additional Rovalpituzumab tesirine administration cycle; Filled arrowhead = Topotecan administration cycle; PTFU = post-treatment follow-up; OS = overall survival

1. Tumor material collection and testing for DLL3 status may occur at any time after initial diagnosis, including outside of the Screening window, depending on completion of the appropriate consent process.
2. Up to two additional cycles of rovalpituzumab tesirine may be permitted for subjects in Arm A meeting certain criteria, as described in Protocol Section 5.3.1.1.
3. Topotecan will be administered until disease progression, unacceptable toxicity or any other reason requiring treatment discontinuation.

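### AESI onset is summarised only by a Kaplan-Meier median that, read per category, will usually be unreached or set by a small retreated tail for pleural effusion in Arm A, and that censors death by implication

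*SAP*

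**What the plan says.** SAP section 12.3 (Time to onset) defines the variable: "Time to onset is the Rx Day of the start date of the first occurrence of AESI". A subject without an AESI is censored at the latest known assessment "or 70 days from the last study drug administered, whichever is earliest". The planned summary is: "Median onset time will be estimated using a Kaplan-Meier method with corresponding 95% CI for the median for each treatment arm". The section does not say whether the first occurrence is counted within each Table 3 category or across all AESIs. It does not mention death. It plans no cumulative incidence, no fixed-time rate, no description of onset among affected subjects, and no test between arms.

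The length of follow-up for these events depends on dosing. Arm A receives "0.3 mg/kg rovalpituzumab tesirine (IV) on Day 1 of a 42-Day cycle for 2 cycles" (SAP section 5.2). Up to two further cycles are possible for subjects who, among other conditions, "have findings indicative of disease progressing (not limited to CNS) at least 12 weeks after the second dose of rovalpituzumab tesirine" (Protocol section 5.3.1.1) and who have had no serosal effusion or edema above Grade 2. Arm B is dosed until progression.

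Protocol section 3.5 gives drug-related incidences for the study drug of 29.4% for pleural effusion and 29.1% for peripheral edema, within a list of the most frequent related terms. Crude incidence of treatment-emergent events is tabulated separately under SAP section 12.2.

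**The concern.** A Kaplan-Meier median exists only if the estimated event probability reaches 50% while subjects are still under observation. For a subject with two doses on schedule, observation for AESIs closes about 70 days after the second dose. The only important identified risk in SAP Table 3 with an all-grade rate in the documents is pleural effusion, at well under 50%.

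Death without the event ends the possibility of having it. Treating it as ordinary censoring estimates onset in a setting where nobody dies. With survival this short that is not a small correction, and its size depends on mortality, which may differ between arms.

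At stake is whether the report tells a reader when the known toxicities occur. This is the only time-to-event safety summary in SAP section 12, and the crude tables elsewhere give no timing.

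**Working it through.** The documents state no figure for AESI onset, so there is nothing to reproduce. The check asks what the planned estimator would return on the documents' own rates.

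**Inputs from the documents**
- Dose days in Arm A: Day 1 and about Day 43 (SAP 5.2). Cap of 70 days after last dose (SAP 12.3).
- Pleural effusion 29.4%, drug-related, crude (Protocol 3.5).
- Median OS 8.67 months (Arm A design value) and 6.5 months (Arm B design value, used here as a pessimistic value for Arm A) (SAP 5.4). The 5.6 months of the third-line Phase 2 study (Protocol 3.3) serves as a lower bound.
- 1 month = 30.4375 days (SAP 11.1.1).
- 444 enrolled at 2:1 (Protocol 8.4), so about 444 × 2/3 = 296 in Arm A.

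**Assumptions not in the documents**
- Constant AESI hazard λ and constant death hazard μ.
- The 29.4% accrues by the end of the window.
- The share of subjects receiving one dose, the share retreated, and the timing of the third dose.

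**Step 1, the window.** Two doses on schedule: 43 + 70 = Day 113. One dose: 1 + 70 = Day 71. Protocol 5.5.6.1.1 allows toxicity delays of up to 28 days before discontinuation, giving 43 + 28 + 70 = Day 141. Retreatment cannot begin before about 43 + 84 = Day 127.

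**Step 2, the curve at Day 113, two doses on schedule.** With μ = ln 2 / (median OS in days), solve λ/(λ+μ) × [1 − exp(−(λ+μ)T)] = 0.294 at T = 113. The Kaplan-Meier event probability, with death censored, is then 1 − exp(−λT). The last column sets 1 − exp(−λT) = 0.5 and gives the crude incidence that would be needed.

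| Median OS (months) | μ per day | Deaths by Day 113 | λ per day | 1 − KM | Excess over 29.4% | Crude incidence needed for a median |
|---|---|---|---|---|---|---|
| 8.67 | 0.002627 | 25.7% | 0.003629 | 33.6% | 4.2 points | 44.0% |
| 6.5 | 0.003504 | 32.7% | 0.003826 | 35.1% | 5.7 points | 42.2% |

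**Step 3, variations.**
- Dose 2 delayed 28 days for everyone (T = 141): 1 − KM is 34.7% (8.67 months) to 36.6% (6.5 months).
- Half of subjects receive one dose (29.4% averaged over T = 71 and T = 113): 1 − KM at Day 113 is 39.1%, 40.5% and 41.4% at median OS 8.67, 6.5 and 5.6 months. The competing-risk incidence is 34.3%, 34.0% and 33.8%, so the excess is about 5 to 8 points. The crude incidence needed for a median falls to between 38.2% and 36.1%.

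**Step 4, whether a median is found.** Simulated trials (296 subjects, 500 runs per setting, median OS 8.67 months, one-dose share 0-50%):
- No retreatment, incidence 29.4% or lower: median reached in 0 to 0.4% of trials.
- 10-20% retreated, 29.4%: median reached in 92-99% of trials, at about Day 158-192, with about 9-19 subjects still at risk.
- 10-20% retreated, 10.3% (the Grade 3 related thrombocytopenia rate, used only as an example of a rarer event): reached in 13-16% of trials, with about 2 at risk.

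**Step 5, the other reading.** If onset means the first AESI of any kind, pleural effusion and peripheral edema alone give 1 − (1 − 0.294)(1 − 0.291) = 49.9% under independence. The bounds are 29.4% (full overlap) and 58.5% (none). A median would then probably be reached, but it would mix unrelated toxicities.

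**The case against.** A reader might infer from Step 2 that the median cannot be reached at all. The documents do not support that. Retreatment and dose delays carry some subjects past Day 113, longer delays may be discussed where benefit is seen, and a modest retreated share usually produces a median in simulation. What stands is that this median rests on few subjects, selected in part for having had no effusion or edema above Grade 2.

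A reader might also extend the point to most AESIs. That is not shown. Table 3 has 19 categories. Several are broad searches (thrombocytopenia, anemia, neutropenia, hepatotoxicity, cutaneous reactions) with no all-grade rate in the documents, and Edema pools 14 preferred terms. The protocol's rates are drug-related only, while the SAP counts treatment-emergent events. Some groups could exceed the 36-44% needed. Arm B has no AESI rate at all.

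A third inference is that the analysis yields no usable or comparable figure. That also overreaches. A median reported as not reached, with a lower confidence limit, is a valid descriptive result. No between-arm comparison of onset is planned. The 4-6 point excess lies in the curve from which the median is read, not in a probability the SAP undertakes to report, and the crude incidence tables are untouched by it.

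Finally, the per-category reading is itself an assumption. This objection stands in full, and it is a reason to clarify the text.

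**Conclusion.** The point holds as a minor weakness in safety reporting. Read per category, the planned median for pleural effusion in Arm A will usually be not reached: 1 − KM is about 34-35% at Day 113, or about 35-37% at Day 141 with a 28-day delay. Otherwise it will come from a small retreated tail. The same is probable for pericardial effusion, generalized edema and photosensitivity, the important identified risks absent from the protocol's list of most frequent terms.

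The underlying curve overstates the event probability by about 4-6 points, or 4-8 if some subjects receive one dose and survival is as short as 5.6 months, because death is censored by implication.

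These sizes rest on constant hazards, on the 29.4% related rate standing in for the AESI rate, and on that rate applying within the window. A treatment-emergent rate above about 42-44% with two doses on schedule would reverse the conclusion for that category. The finding does not extend to the broad AESI groups or to Arm B. No hypothesis test, primary endpoint or study decision depends on it.

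**What to change.** In SAP section 12.3:

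1. State that onset is analysed separately for each Table 3 category.
2. Name death without the AESI as a competing event. Replace or supplement the Kaplan-Meier median with the Aalen-Johansen cumulative incidence and 95% CI, by arm, at fixed Rx Days such as 43, 71 and 113, showing numbers at risk.
3. Add the median and range of onset day among subjects who had the event, labelled as descriptive only.
4. Note beside the table that observation windows still differ between arms, because of the 70-day cap and because Arm B is dosed to progression. The competing-risk estimate deals with death but does not remove that difference.

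The cost is a few sentences in a SAP that describes itself as a draft and a little extra programming. No new data are needed.
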